1 INTRODUCTION

1.1 STUDY DESIGN

This is a Phase 4, 16 week, prospective, multicenter, interventional, open-label, single-arm study in insulin-naïve participants with very uncontrolled type 2 diabetes mellitus (T2DM) using blinded continuous glucose monitoring (CGM). The primary endpoint will assess the change of time in range (70-180mg/dL) between baseline and week 16 as measured by CGM in participants initiated on Soliqua 100/33. Background GLP-1RA (oral or injectable) and DPP-4i therapies will be discontinued prior to Soliqua 100/33 administration and sulfonylureas will be down-titrated by 50% when starting Soliqua 100/33. Continuous glucose monitoring measures will allow clinicians to frequently observe changes in glycemic control and variability including measures such as time in range (TIR), time below range (TBR) and time above range (TAR) with more granularity than the measure of HbA1c% alone. The Freestyle Libre Pro is a flash glucose monitoring device that collects glucose values every 15 minutes for up to 14 days. These values are charted into a single daily view, irrespective of the numbers of glucose values measured to provide a view of glycemic control and variability and assist clinicians for management of patients with diabetes.

[figure not shown]
All eligible participants will undergo 14 days of blinded continuous CGM monitoring and a mixed-meal tolerance test (MMTT) during the run-in period while on background medications. Soliqua 100/33 will be initiated, and dose will be adjusted during the 12-week titration period, at the investigator's discretion, until the desired fasting self-measured plasma glucose (SMPG) value (80-100 mg/dL) is achieved.

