4.3 PRIMARY ENDPOINT(S) ANALYSIS

4.3.1 Definition of endpoint(s)

The primary endpoint is the difference from baseline to week 16 in the percentage of TIR of 70-180 mg/dL using 14 days of CGM data at baseline. The percentage of time spent in the glycemic target range will be calculated as 100 times the number of recorded measurements in the glycemic target range, (70-180 mg/dL) inclusive, divided by the total number of recorded measurements. All the efficacy assessments collected during the study will be used, including those obtained after IMP discontinuation or introduction of rescue therapy. Regardless of intercurrent events at week 16, the value for the mean change in the percentage of TIR will be used.

CGM data

CGM compliance is defined as:

1. at least 8 out of 14 days (not necessarily consecutive) have 100% of evaluable CGM data per 24-hour period (total of 768 records on 8 days) OR
2. at least 9 out of 14 days (not necessarily consecutive) have $\geq 89\%$ of evaluable CGM data per 24-hour period (total of 768 records on 9 days and at least 9 days with 85 records minimum) OR
3. at least 10 out of 14 days (not necessarily consecutive) have at least $\geq 80\%$ of evaluable CGM data per 24-hour period (total of 768 records on 10 days and at least 10 days with 77 records minimum)

during baseline (the run-in period) as well as week 16.

During the run-in period or end of treatment period, CGM device reinsertion will be allowed for participants who do not meet the compliance criteria over a 14-day period as a result of premature sensor failure.

Baseline will be defined as the first 14 evaluable days of evaluable CGM data prior to first day of treatment and referred to as the run-in period in the graphical study design. An evaluable day is defined as a 24-hour period with $\geq 80\%$ non-missing measurements. Only evaluable days will be included in the analysis. Week 16 will be defined as the first 14 evaluable days of evaluable CGM data starting at day 95 or later.

The first day of CGM data will start at time of device insertion and subsequent days will start every 24 hours. If the device is re-inserted, device with the most compliant data will be used and if neither session is evaluable, the combined data from both sessions will be used as evaluable data. For subsequent reinsertions, the day will start at time of reinsertion.

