Unless otherwise specified, outcome variables based on CGM data will use subjects in the efficacy analysis set with compliant data at baseline.

Percent time in the glucose range is defined as the total number of 15-minute increments where a participant's blood glucose falls within range of ≥ 70 to ≤ 180 mg/dL (≥ 3.9 to ≤ 10 mmol/L) divided by the total number of observed 15-minute increments in that period. Percent time in range will be calculated for baseline (run-in) and for week 16.

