- Change (%) from baseline (run-in) to week 16 in TAR (>180 mg/dL). The percentage of time spent above the glycemic target range will be calculated as 100 times the total number of 15-minute increments of CGM data where a participant's blood glucose falls above normal range (>180 mg/dL) in a 14-day period divided by the total number of 15-minute increments read (up to 1344 15-minute increments). This will be calculated for

baseline (run-in) and for week 16 and the change will be reported. The alternative hypothesis to be tested is that the TAR differs between baseline and week 16. A two-sided 95% CI will be presented.

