4.5 TERTIARY/EXPLORATORY ENDPOINT(S) ANALYSIS

4.5.1 Definition of endpoint(s)

Mean changes for continuous outcomes for additional measures of glycemic control and variability in participants with T2DM:

- Change (mg/dL) from baseline (run-in) to week 16 in mean of daily difference [MODD] of glucose levels. Using the formula: $\frac{\sum_{t=0}^{t=95} |[Day_{j+1,t} - Day_{j,t}]|}{\text{number of paired timepoints}}$ where t =time period in the 24 hour day by 15 minute intervals and j = day to calculate MODD for each participant 13 times comparing Day 2 to Day 1, up to Day 14 to Day 13 for Baseline and for week 16. The average absolute daily differences at each 15-minute interval of CGM data will be summarized using descriptive statistics. Two-sided 95% CI will be presented.
- Change (%) from baseline (run-in) to week 16 in TAR >250 mg/dL. The percentage of time spent above the glycemic target range will be calculated as 100 times the number of the total number of 15-minute increments of CGM data where a participant’s blood glucose falls above normal range (>250 mg/dL) in a 14-day period divided by the total number of 15-minute increments read (1344 number of 15-minute increments). This will

be calculated for baseline and for week 16 to report the difference. A two-sided 95% CI will be presented.

- Change (%) from baseline (run-in) to week 16 in TBR <70 mg/dL. The percentage of time spent below the glycemic target range will be calculated as 100 times the number of the total number of 15-minute increments from CGM data where a participant's blood glucose falls below normal range (<70 mg/dL) in a 14-day period divided by the total number of 15-minute increments read (1344 number of 15-minute increments). This will be calculated for baseline and for week 16 to report the difference. A two-sided 95% CI will be presented.
- Correlation of change in percentage of TIR [70 – 180 mg/dL] and change in PRO from baseline (run-in) to week 16. Analysis will be done between each of the 4 domains (well-being, medical control, lifestyle, and convenience), PRO overall, and change in TIR. The purpose of finding the correlation of change from baseline to week 16 for percentage of TIR and PRO is to determine the relationship between those two continuous variables.

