- Correlation of percentage of TIR [70 – 180 mg/dL] and HbA1c percentage achieved at week 16. The correlation of percentage of TIR and HbA1c achieved at week 16 will estimate the relationship between the two variables.
- Association of participants reaching 60 units/day insulin glargine U100 and TIR > 70%.
- Change in HbA1c percentage from baseline (run-in) to week 16. The alternative hypothesis to be tested is that the HbA1c will decrease from baseline to week 16. A two-sided 95% CI will be presented. This analysis will be based on participants in the enrolled set who have non-missing outcomes at baseline and week 16.
- Change in the percentage from baseline (run-in) to week 16 for TITR (70-140 mg/dL). The end point will determine the percentage of time spent in the glycemic tight target range. This is calculated as 100 times the number of recorded measurements in the glycemic target range, (70-140 mg/dL) inclusive, divided by the total number of recorded measurements per time block and comparing week 16 to baseline over a 14-day period to determine change. A two-sided 95% CI will be presented.
- Proportion (%) of participants with TIR (70–180 mg/dL) > 70% each day at week 16. To calculate the proportion of participants achieving TIR of >70% each day, a sum of the number of participants with more than 67 15-minute intervals with glucose values in range per day for all compliant days divided by the total number of participants. The endpoint will be calculated using all CGM glucose readings available throughout each day for two weeks at the end of study. As this is a binary outcome the endpoint will be summarized with proportions and 95% CI using the Clopper Pearson exact method. A two-sided 95% CI will be presented.
- Proportion (%) of participants with $\geq 5\%$ absolute improvement from baseline in TIR (70-180 mg/dL). Absolute improvement is defined as an increase in TIR from baseline to week 16. To calculate the proportion of participants achieving $\geq 5\%$ in TIR absolute improvement from baseline a sum of the number of participants with a positive percent change $\geq 5\%$ will be divided by the total number of participants. The endpoint will be calculated using all CGM glucose readings available throughout each day for each two-

week time blocks. As this is a binary outcome the endpoint will be summarized with proportions and 95% CI using the Clopper Pearson exact method. A two-sided 95% CI will be presented.

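### Daily TIR >70% is judged by a full-day count of 67 readings even on incomplete days, and the denominator for TAR >250 and TBR <70 is described in two conflicting ways

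*SAP*

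**What the plan says.** The sensor "collects glucose values every 15 minutes for up to 14 days" (SAP 1.1), so a full day holds 96 readings and a full period 1344.

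The SAP sets its CGM percentages in different ways:

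- Primary TIR is the in-range count "divided by the total number of observed 15-minute increments in that period" (SAP 4.3.1).
- Key secondary TAR >180 is "divided by the total number of 15-minute increments read (up to 1344 15-minute increments" (SAP 4.4.1.1).
- Exploratory TAR >250 and TBR <70 both divide by the "total number of 15-minute increments read (1344 number of 15-minute increments" (SAP 4.5.1). The qualifier *up to* is absent.
- Exploratory TIR >70% each day uses no percentage. It requires "more than 67 15-minute intervals with glucose values in range per day for all compliant days" (SAP 4.5.1).

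Incomplete data are expected. SAP 4.3.1 treats a day as evaluable with at least 80% of its readings and analyses evaluable days only. A participant can comply with a "total of 768 records on 10 days and at least 10 days with 77 records minimum".

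**The concern.** A fixed count or denominator is right only when no reading is missing, and the compliance rule explicitly admits missing readings.

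For daily TIR, a count of 67 is 70% of a complete day. On a shorter day it becomes a stricter criterion than the endpoint's name. It must be met on every compliant day, so one incomplete day can fail a participant who was above 70% throughout.

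For TAR >250 and TBR <70, two programmers following the same sentence could use different denominators. With a literal 1344, missing readings are in effect counted as not above 250 and not below 70. TBR would no longer share a scale with TIR and TAR >180, and those three would not sum to 100%. Differences in sensor completeness between run-in and Week 16 would leak into the change from baseline.

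**Working it through.** **Inputs.** One reading per 15 minutes for up to 14 days (SAP 1.1); evaluable day at least 80% of readings, 768-reading floor, and 85 and 77 readings as daily minima in the compliance options (SAP 4.3.1); 1344 and more than 67 (SAP 4.5.1). I take *compliant days* in the daily TIR rule to mean evaluable days.

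**The plan's own figures.** 24 × 4 = 96 readings a day and 14 × 96 = 1344, as stated. 0.70 × 96 = 67.2, so >70% of a full day needs 68 readings, which matches more than 67. Both figures are correct for complete data only.

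**Daily TIR.** Share demanded = 68 / readings that day. The smallest count that is truly >70% is the next whole number above 0.70 × readings.

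| Readings that day | Rule as written | Count needed for >70% |
|---|---|---|
| 96 | 68/96 = 70.8% | 68 |
| 85 | 68/85 = 80.0% | 60 |
| 77 | 68/77 = 88.3% | 54 |

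The demanded share never falls below that of a full day, so the error runs one way. A participant with 80% in range on a 77-reading day has about 0.80 × 77 = 61.6 in-range readings and fails, although 54 would be enough. As an illustration, if readings were independent with true TIR 80%, the chance of passing one day would be 0.989 with 96 readings, 0.564 with 85 and 0.040 with 77. A proportional rule gives 0.989, 0.987 and 0.986. Real CGM readings are serially correlated, so only the pattern matters here.

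**TAR >250 and TBR <70 levels, if 1344 is literal.** Reported % = true % × readings / 1344. The true levels of 30% and 4% are assumptions.

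| Readings | Factor | TAR >250, true 30% | TBR, true 4% |
|---|---|---|---|
| 1344 | 1.000 | 30.0% | 4.0% |
| 14 × 77 = 1078 | 0.802 | 24.1% | 3.2% |
| 768 (floor) | 0.571 | 17.1% | 2.3% |

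**Changes, if 1344 is literal.** Reported change = (Week 16 % × Week 16 readings − baseline % × baseline readings) / 1344. The low-completeness case is 10 × 77 = 770 readings; the glucose levels are again assumptions.

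| Readings, baseline / Week 16 | TAR >250 30%→10% (true −20) | TAR >250 30%→30% (true 0) | TBR 1%→3% (true +2) |
|---|---|---|---|
| 770 / 770 | −11.5 | 0 | +1.1 |
| 1344 / 770 | −24.3 | −12.8 | +0.7 |
| 770 / 1344 | −7.2 | +12.8 | +2.4 |

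**Composite endpoint.** SAP 4.5.1 also counts participants with TIR >70% and TBR <4%, without giving a TBR denominator. If a literal 1344 were carried over, the true TBR that reports as 4% would be 4 × 1344/768 = 7.0% at the floor and 4 × 1344/1078 = 5.0% at 1078 readings.

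**The case against.** The strongest reply concerns the denominator. The operative words for TAR >250 and TBR <70 are increments read, which already means recorded readings; 1344 is a parenthesis. The TAR >180 bullet has the same phrase with *up to*, and TIR, TIR by time block and time in tight range all use observed or recorded readings. The natural inference is that two words were dropped. This stands. A reader might infer that the SAP fixes the denominator at 1344; the text does not settle that. What it contains is a contradiction.

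A reader might also infer that missing readings understate these endpoints in general. That is too strong. TAR >250 and TBR <70 are analysed as changes from baseline. Under a literal 1344 only the levels are always understated; the change can move either way, as the table shows. The 0.57 factor belongs to a participant at the floor, and the documents give no expected completeness.

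Nor do the documents support reading this as a flaw in safety reporting. Hypoglycemia events are classified from the hypoglycemia eCRF page (SAP 4.7.3), not from CGM TBR.

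For daily TIR, one can say that the endpoint's name and its reference to all available readings show a proportional intent, and that the error works against the product. Both are true, but the stated rule is still a count, and nothing elsewhere in the SAP overrides it.

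**Conclusion.** The daily TIR rule is wrong as written. It demands 80.0% on an 85-reading day and 88.3% on a 77-reading day instead of >70%, and can only turn true responders into non-responders. How many participants are affected depends on sensor completeness, which the documents do not give.

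The TAR >250 and TBR <70 wording contradicts itself and the parallel definitions. It does harm only if 1344 is programmed literally. Levels would then be scaled by 0.57 to 1.0, and changes could be shrunk, inflated or created. The size of any distortion in a change rests on the assumed glucose levels and on how completeness differs between periods.

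All affected endpoints are tertiary or exploratory and outside the testing hierarchy in SAP 4.6. Primary TIR, key secondary TAR >180 and the sample size are unaffected. The correction is worth making before the analysis is programmed, but no confirmatory conclusion turns on it.

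**What to change.** In SAP 4.5.1:

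1. Define daily TIR as in-range readings divided by the readings recorded that day, required to exceed 70% on each evaluable day. Delete the count of 67, and replace *compliant days* with the evaluable-day term from SAP 4.3.1.
2. In both the TAR >250 and TBR <70 bullets, give the denominator as readings recorded on evaluable days, up to 1344.
3. State that TBR in the composite responder endpoints uses that same denominator.

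The cost is SAP wording and matching derivation code. No data collection, sample size or testing order changes.

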Time in range (TIR) is one of the metrics derived from CGM and is increasingly utilized to assess glycemic control. It can correlate with HbA1c values as well as the risk of diabetes-related complications (both microvascular and macrovascular). The International Consensus Report on "clinical targets for CGM interpretation" has identified "TIR" as a metric providing more actionable information than HbA1c and has defined targets for clinical use (Battelino et al 2019). For example, in patients with uncomplicated T2DM whose HbA1c targets are <7%, the recommended TIR (for a target range of 70-180 mg/dL) is >70% of the readings.

Soliqua 100/33 is indicated as an adjunct to diet and exercise to improve glycemic control in adults with T2DM (Soliqua 2019). The 2021 Standards of Medical Care in Diabetes from the ADA (ADA 2021a; ADA 2021b) recommends the use of fixed-ratio combinations when the combination of individual components is indicated, such as when a GLP-1 RA is added to basal insulin or vice versa. The ADA 2021 Standards also recommend dual combination therapy in individuals with HbA1c values $\geq 1.5\%$ from their glycemic target (ADA 2021b). Correlations of HbA1c and TIR indicate that CGM glucose readings of patients with an HbA1c $\geq 9\%$ are in range 40% of the time or less, compared with the 70% TIR associated with an HbA1c of 7% (Battelino et al 2019). Although there are currently no studies using CGM measurements to capture glycemic excursions and variability related to Soliqua 100/33, a post hoc analysis demonstrated improvement in all measures of glycemic variability compared with its individual components (eg, lixisenatide or insulin glargine U100), assessed by 7-point blood glucose profiles. These findings were attributable to Soliqua 100/33's complementary mechanisms of action, which demonstrate reductions in both fasting and postprandial hyperglycemia (Aronson et al 2019).

The current study is intended to replicate these results using CGM to measure TIR and glycemic variability in a patient population with very uncontrolled T2DM (HbA1c \geq 9%-13%), who are most likely to benefit from a fixed-ratio combination approach, such as Soliqua 100/33.

The primary objective of this study is to demonstrate an improvement in the percentage of TIR from baseline to the end of the study (16 weeks) in insulin-naïve patients with very uncontrolled (HbA1c \geq 9%-13%) T2DM on 2+ OADs with or without GLP-1 RAs.

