Tertiary/exploratory	
 To evaluate the impact of Soliqua 100/33 on additional measures of glycemic control and variability in participants with T2DM 	
 Change (mg/dL) from baseline to week 16 in mean of daily difference (MODD) Change (%) from baseline to week 16 in TAR (>250 mg/dL) Change (%) from baseline to week 16 in time below range (TBR); <70 mg/dL) Correlation of change in the percentage of TIR (70-180 mg/dL) and change in patient reported outcome (PRO) from baseline to week 16 Correlation of percentage of TIR (70-180 mg/dL) and HbA1c percentage achieved at week 16 Association of participants reaching 60 units/day insulin glargine U100 and TIR >70% Change in HbA1c percentage from baseline to week 16 Change in the percentage from baseline to week 16 for Time in Tight Range (TITR)(70-140 mg/dL) Proportion of participants with TIR (70–180 mg/dL) > 70% of each day at week 16 Proportion of participants with ≥5% absolute improvement from baseline to week 16 in TIR (70–180 mg/dL) Proportion of participants with ≥10% absolute improvement from baseline to week 16 in TIR (70–180 mg/dL) Proportion of participants with improvement in HbA1c >0.5% points from baseline to week 16 without an increase in TBR (<54 mg/dL) of >0.5% Proportion of participants with ≥10% absolute improvement from baseline to week 16 in TIR (70–180 mg/dL) without an increase in TBR (<54 mg/dL) of >0.5% Proportion of participants with TIR (70–180 mg/dL) > 70% per day and TBR (<70 mg/dL) < 4% per day at week 16

Objectives	Endpoints

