- Proportion (%) of participants with $\geq 10\%$ absolute improvement from baseline in TIR (70-180 mg/dL). Absolute improvement is defined as an increase in TIR from baseline to week 16. To calculate the proportion of participants achieving $\geq 10\%$ absolute improvement in TIR from baseline a sum of the number of participants with a positive percent change $\geq 10\%$ are divided by the total number of participants. The endpoint will be calculated using all CGM glucose readings available throughout each day for each two-week time blocks. As this is a binary outcome the endpoint will be summarized with proportions and 95% CI using the Clopper Pearson exact method. A two-sided 95% CI will be presented.
- Proportion (%) of participants with improvement in HbA1c $>0.5\%$ points without an increase in TBR (<54 mg/dL) of $>0.5\%$. Improvement is defined as an increase in HbA1c from baseline to week 16. To calculate the proportion of participants achieving $>0.5\%$ improvement of HbA1c from baseline and with $< 0.5\%$ change in TBR participants will be summed then divided by the total number of participants. The endpoint will be summarized based upon CGM data reporting both percentages and 95% CI using the Clopper Pearson exact method. A two-sided 95% CI will be presented.
- Proportion of participants with $\geq 10\%$ absolute improvement from baseline in TIR (70-180 mg/dL) without an increase in TBR (<54 mg/dL) of $>0.5\%$. Absolute improvement is defined as an increase in TIR from baseline to week 16. A sum of participants with both $\geq 10\%$ of improvement from baseline in TIR and no increase in TBR of more than 0.5% will be divided by the total number of participants. The endpoint will be summarized based upon CGM data reporting both percentages and 95% CI using the Clopper Pearson exact method. A two-sided 95% CI will be presented.
- Proportion of participants with TIR (70–180 mg/dL) $>70\%$ and TBR (<70 mg/dL) $<4\%$ at Week 16. To calculate the proportion of participants achieving TIR $>70\%$ and TBR $<4\%$, a sum of the number of participants with both TIR $>70\%$ and TBR $<4\%$ divided by the total number of participants. The endpoint will be summarized based upon CGM data reporting both percentages and 95% CI using the Clopper Pearson exact method. A two-sided 95% CI will be presented.

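### The exploratory TIR >70% responder rule makes the result depend on sensor wear, and the SAP defines its TIR/TBR composite in two different ways

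*SAP*

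**What the plan says.** SAP 4.5.1 gives the counting rule for the TIR >70% responder: the number of participants having more than 67 intervals of 15 minutes with "glucose values in range per day for all compliant days divided by the total number of participants". The matching row of SAP Table 2 (section 1.2) reads TIR "> 70% of each day at week 16". The two places agree that every counted day must pass.

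For the composite with time below range, Table 2 sets both parts by day: TIR "> 70% per day and TBR (<70 mg/dL) < 4% per day at week 16". SAP 4.5.1 describes the numerator only as "a sum of the number of participants with both TIR" above 70% and TBR below 4%, at Week 16. It states neither a per-day nor a whole-period condition.

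The general definition in SAP 4.3.1 divides in-range increments by observed increments and adds: "Percent time in range will be calculated for baseline (run-in) and for week 16". The same section calls a day evaluable when at least 80% of its measurements are present, and states: "Only evaluable days will be included in the analysis". SAP 4.5.1 calculates TBR below 70 mg/dL over a 14-day period. CGM compliance (SAP section 3 and 4.3.1) can be met by 8 days of 96 records, 9 days of at least 85, or 10 days of at least 77. Up to 14 evaluable days are used.

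The clinical target cited in Protocol 1.2 is stated over readings: "the recommended TIR (for a target range of 70-180 mg/dL) is >70% of the readings".

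**The concern.** A rule that must be met on every day is harder to meet the more days a participant supplies. Two participants with the same glucose control can be classified differently because one sensor lasted longer. The daily cut-off is a fixed count rather than a share of what was recorded, so gaps within a counted day act in the opposite direction. The reported proportion then mixes glycaemic control with device performance.

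The composite adds a second problem. Anyone who meets TIR >70% and TBR <4% should also meet TIR >70%. If the stand-alone endpoint is judged day by day and the composite over the period, that nesting is lost, and the results could show more people meeting two conditions than meeting one of them.

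**Working it through.** **1. The SAP's own cut-off.** One reading every 15 minutes gives 96 per day, and 0.70 × 96 = 67.2. More than 67 therefore means at least 68, and 68/96 = 70.8%. The figure of 67 reproduces for a complete day.

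**2. The same count on incomplete days that still qualify** (record minimums from SAP section 3):

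| Records in the day | Share needed under the fixed count |
|---|---|
| 96 | 68/96 = 70.8% |
| 85 | 68/85 = 80.0% |
| 77 | 68/77 = 88.3% |

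A day with 65 of 77 readings in range (84.4%) fails. Judged as a share of recorded readings, a 77-record day would need 54 in range (70.1%).

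**3. Number of counted days.** Removing a day can never turn a pass into a fail, so the direction needs no model. For size, assume independent days with success probability q, so that the pass rate is q^k over k days:

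| q (assumed) | k = 8 | k = 14 |
|---|---|---|
| 0.80 | 0.168 | 0.044 |
| 0.90 | 0.430 | 0.229 |
| 0.95 | 0.663 | 0.488 |

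**4. Both effects in a population.** None of the inputs here comes from the documents. Person-level TIR is normal with mean 65 and SD 20, day-to-day SD is 12, days are independent within a person, and values are truncated to 0–100.

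| Week 16 data | Each-day rule, fixed count | Each-day rule, share of recorded readings | Period TIR >70% |
|---|---|---|---|
| 14 days × 96 | 10.9% | 10.9% | 40.1% |
| 8 days × 96 | 14.5% | 14.5% | 40.3% |
| 14 days × 77 | 0.5% | 11.5% | 40.1% |
| 10 days × 77 | 1.0% | 13.7% | 40.2% |

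Losing whole days raises the each-day rate (14.5 − 10.9 = 3.6 points). Losing readings within days nearly removes it. The period rate hardly moves. With assumed means of 55 to 75 (person-level SD 25 to 15) and day-to-day SDs of 8 to 15, the each-day rate with 14 full days runs from 5.3% to 28.5%, against roughly 27% to 63% for period TIR.

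**5. When the composite exceeds its component.** Suppose the stand-alone endpoint is each-day (10.9%) and the composite is period-based. The composite is larger once more than 10.9/40.1 = 27% of period TIR responders also meet TBR <4%. If both parts of the composite are applied per day on the same counting rule, as in Table 2, the composite is a subset of the each-day responders and cannot exceed them.

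**The case against.** The strongest defence is that the each-day requirement appears in both Table 2 and 4.5.1. It therefore looks deliberate: a stricter exploratory endpoint that the SAP never presents as the cited 70% target. Table 2 also makes the composite per day, which preserves nesting. That much is fair. It means that one cannot say the plan misreports the clinical target, or that the two results will conflict. It does not remove the dependence on wear, and it does not settle which text a programmer should follow for the composite.

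Three stronger readings are tempting, and the documents do not support them.

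- A reader might infer that poor sensor wear in general raises the response. That holds only for lost whole days. The 8-day route requires complete days, and under the fixed count missing readings lower the response. The denominator, described only as the total number of participants, is also undefined. If participants without compliant Week 16 data stay in it, poor wear lowers the proportion further. SAP 4.5.2 excludes such participants, but in a paragraph on continuous and correlation analyses.
- A reader might infer that 4.5.1 prescribes a whole-period composite. It is silent. The period reading is an inference from the TIR definition in 4.3.1 and the TBR definition in 4.5.1.
- A reader might extend the point to the table relating TIR >70% to 60 units/day. No per-day condition is attached there, and 4.3.1 already supplies a Week 16 percentage, so no defect is shown.

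The illustrative rates rest on assumed means and SDs and on independent daily variation. Positive correlation between days would raise the each-day pass rate and usually narrow the gap between 8 and 14 days.

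**Conclusion.** The point holds in two limited parts. First, the stand-alone responder proportion depends on sensor wear in opposite directions: fewer counted days make passing easier, and gaps within counted days make it harder (70.8% in range needed on a full day, 88.3% on a 77-record day). These percentages and both directions follow from the SAP alone. The population rates are illustrations under stated assumptions. Second, Table 2 and 4.5.1 disagree on the composite. If 4.5.1 is programmed over the Week 16 period, the composite can exceed the stand-alone TIR proportion; if Table 2 is followed with the same counting rule, it cannot.

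Both endpoints are exploratory and outside the testing hierarchy in SAP 4.6. The primary and key secondary analyses and the control of type I error are unaffected. The correction is worth making because the definitions conflict and the change is small.

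**What to change.** Reconcile the two Table 2 rows and the two 4.5.1 definitions as follows.

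- TIR responder: more than 70% of recorded readings in 70–180 mg/dL, over all evaluable days in the Week 16 period.
- Composite: that same condition, plus fewer than 4% of the same readings below 70 mg/dL.
- Denominator: one stated denominator for both, saying whether participants without compliant Week 16 data are included.

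This makes the composite a true subset of the TIR responders, removes the fixed count, and agrees with the readings-based target in Protocol 1.2. If the each-day view is of interest, keep it as a descriptive proportion of days meeting the target. The 60-unit table needs only to use the same Week 16 TIR.

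The cost is SAP wording and one programming change. No new data are needed.
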